2.1 Data analysis general information

Data will be listed and summarized according to GSK Integrated Data Standards Library (IDSL) reporting standards. Formatting for dates, times, and decimal places will follow GSK standards except where specified.

The final analyses will be performed by [REDACTED]. The currently supported version of Statistical Analysis System (SAS®) will be used to perform all data analyses, and generate tables, figures, and listings.

2.1.1 Data included in the analysis

All data up to the time of study completion (i.e. 24 weeks of lapatinib and capecitabine treatment) or withdrawal from the study will be included in the final analysis, regardless of duration of treatment.

All data with an assessment date or event start date (e.g. vital sign assessment date or start date of an adverse event) prior to or on the cut-off date will be included in the analysis. Any data

collected beyond the cut-off date will not be included in the analysis and will not be used for any derivations. For the final analysis the database lock date will be used as cut-off date.

All events with start date before or on the cut-off date and end date after the cut-off date will be reported as ‘continuing at the cut-off date’. The same rule will be applied to events starting before or on the cut-off date and not having documented end date. This approach applies, in particular, to adverse event and concomitant medication reports. For these events, the end date will not be imputed and therefore will not appear in the listings.

2.1.2 General analysis conventions

Unless specified otherwise, categorical data (e.g., gender, race, etc.) will be summarized by means of contingency tables by treatment group; a missing category will be included as applicable. Percentages will be calculated using the number of subjects in the relevant population as the denominator. Continuous data (e.g., age, body weight, etc.) will be summarized by appropriate descriptive statistics (i.e. mean, standard deviation, minimum, median, and maximum) by treatment group.

Unless specified otherwise, all listings will be sorted by treatment group, center, subject number, and then by visit date and time, if applicable. Only visits at Cycle 2 and 4 are mandated, other visits are as per clinical practice. All available data will be included in listings, including data from unscheduled visits.

All laboratory data will be presented in GSK’s standard units for reporting.

Planned (nominal) assessment times relative to study drug dosing will be used in all summaries and analyses.

Assessment windows will not be defined for the purpose of classifying measurements obtained outside scheduled assessment times.

Note: although octreotide is administered twice, once 7 days before the first cycle of lapatinib and capecitabine and then 28 days later, assessments will be entered as cycles to correspond to the lapatinib plus capecitabine assessments. For this purpose a cycle corresponds to 3 weeks of lapatinib and capecitabine.

Deviations from the analyses in the SAP will be identified in the CSR.

2.1.3 General definitions

2.1.3.1 Investigational drug and study treatment

Investigational drug, will refer to the Octreotide only. Whereas, *study treatment* will refer to Octreotide + Lapatinib + Capecitabine and Lapatinib + Capecitabine.

The following treatment descriptors will be used on all applicable displays:

Table 2-1 Treatment descriptors of investigational drug

Treatment Group Description	Data Display	Order of Treatment Groups
Octreotide+Lapatinib+Capecitabine	Octreotide+Lap+Cap	1

Lapatinib+ Capecitabine	Lap+Cap	2
-------------------------	---------	---

2.1.3.2 Reference start date

There are three reference start dates:

- Age is an eligibility requirement and therefore the reference start date for age is the date of screening.
- The safety reference start date is the date of a subject receiving the first dose of study treatment (i.e., octreotide, lapatinib or capecitabine).
- The efficacy reference start date is the date of randomization and will be used to calculate study day for efficacy measures and baseline characteristics.

The reference start date for all other, non-safety assessments (i.e., tumor assessment, death, disease progression, tumor response, ECOG performance status, and patient reported outcomes (PRO)) is the date of randomization.

2.1.3.3 Date of first/last administration of study drug/study treatment

• **Date of first administration of study drug**

The date of first administration of investigational drug is defined as the first date when a nonzero dose of investigational drug is administered and recorded on the Dosage Administration Record (DAR) (e)CRF. The date of first administration of study drug will also be referred as start of investigational drug.

• **Date of last administration of study drug**

The date of last administration of investigational drug is defined as is the last date when a nonzero dose of investigational drug is administered and recorded on DAR eCRF. The date of last administration of investigational drug will also be referred as end of investigational drug.

• **Date of first administration of study treatment**

The date of first administration of study treatment is derived as the first date when a nonzero dose of any component of study treatment was administered as per the Dosage Administration (e)CRF. (Example: if 1st dose of Octreotide is administered on 05-Jan-2015, and 1st dose of combination partner is administered on 03-Jan-2015, then the date of first administration of study treatment is on 03-Jan-2015).

• **Date of last administration of study treatment**

The date of last administration of study treatment is derived as the last date when a nonzero dose of any component of study treatment was administered as per Dose Administration (e)CRF. (Example: if the last Octreotide dose is administered on 15-Apr-2014, and the last dose of a combination partner is administered on 17-May-2014, then the date of last administration of study treatment is on 17-May-2014).

2.1.3.4 Study day

The study day, describes the day of the event or assessment date, relative to the reference start date. There is no study day 0.

The study day is defined as:

- The date of the event (visit date, onset date of an event, assessment date etc.) – reference start date + 1 if event is on or after the reference start date;
- The date of the event (visit date, onset date of an event, assessment date etc.) – reference start date if event precedes the reference start date.

The study day will be displayed in the data listings. If an event starts before the reference start date, the study day displayed on the listing will be negative.

2.1.3.5 Duration/Elapsed Time/Time unit

Durations (e.g., the duration of an adverse event, duration of exposure, duration of episodes of diarrhoea) are calculated as the stop date minus the start date +1.

For elapsed time (e.g., the time since initial diagnosis):

- If the reference start date is on or after the event date, then the elapsed time is the reference start date minus the event date + 1.
- If the reference start date is before the event date then the elapsed time is the reference start date minus the event date.

A year length is defined as 365.25 days. A month length is 30.4375 days (365.25/12). If duration is reported in months, duration in days will be divided by 30.4375. If duration is reported in years, duration in days will be divided by 365.25.

2.1.3.6 Baseline

Baseline is defined as the most recent, non-missing value prior to receiving the first dose of study treatment (octreotide, lapatinib or capecitabine).

For subjects who did not receive any study treatment (i.e. octreotide, lapatinib or capecitabine) during the study, baseline will be defined as the latest, non-missing collected value.

If patients have no value as defined above, the baseline result will be missing.

2.1.3.7 Change from baseline

Change from baseline will be presented for safety data as described in the relevant sections.

Change from baseline is calculated as:

- visit value - baseline value, if records occur after baseline, or
- missing, if either the baseline or visit value is missing.

2.1.3.8 Multiple assessments

All data will be analysed according to the nominal visit date for which it was reported (that is, no visit windows will be applied during dataset creation). Unscheduled data will only be included in the display sections that report worst-case post-baseline.

If multiple assessments on different days are reported for the same scheduled assessment, then the latest assessment for that scheduled assessment will be analysed.

If multiple assessments are reported on the same date for the same scheduled planned time, then the mean of the multiple measurements reported for the same date will be analysed. For example, for ECG data where 3 assessments are collected for each scheduled planned time, the first 3 measures will be used to compute the mean values for ECG intervals at each scheduled planned time.

Data from all assessments (scheduled and unscheduled), including multiple assessments, will be included in listings.

2.1.3.9 Last contact date

The last contact date will be derived for subjects not known to have died at the analysis cut-off using the last complete date among the following:

- “When was subject last seen or heard alive?” collected on the ‘DEATH’ eCRF.
- All assessment dates (e.g. tumor assessment, laboratory collection dates, vital signs assessment, performance status/PRO assessment, ECG assessment). Note, only a true on study assessment date or patient contact date will be used. If there is a visit date without evidence of any actual assessment performed that date will not be used.
- Medication dates including study medications, concomitant medications, and anti-neoplastic therapies administered after study treatment discontinuation (with non-missing medication/procedure term).
- Adverse event dates (with non-missing verbatim AE term present).
- Randomization date.
- Date of subject discontinuation from ‘Conclusion Details’ eCRF.

The last contact date is defined as the latest complete date from the above list or the cut-off date whichever comes first. The cut-off date will not be used for last contact date, unless the patient was seen or contacted on that date. No date post cut-off date will be used. Completely imputed dates (e.g. the analysis cut-off date programmatically imputed to replace the missing end date of a dose administration record) will not be used to derive the last contact date. Partial date imputation is allowed for event (death)/censoring is coming from ‘Death’ eCRF.

The last contact date will be used for censoring of subjects in the analysis of overall survival.

2.1.3.10 On-treatment assessment/event

All on-treatment assessments/events are any assessments/events obtained in the time interval:

[date of first administration of study treatment, date of last administration of study treatment +28 days], i.e., inclusive lower and upper limit.

2.1.3.11 Study Time Periods for Concomitant Medications and Blood and Blood Supportive Care Products

Concomitant Medication and Blood and Blood Supportive Care Product start and end dates will be assigned to study time periods in relation to first dose of study treatment (octreotide, lapatinib or capecitabine as applicable). The start date reference time flag variables and end

date reference time flag variables will be added to the concomitant medications and blood and blood supportive products datasets, respectively.

- **Start relative to treatment:** Assign to 'BEFORE' if start date is prior to first dose of study treatment start date, if subject has not taken any study treatment, or start date is missing and end date is before study treatment start date. Else assign to 'DURING' if the start date falls into the on-therapy period (defined as the time from first dose of study treatment to the last dose date of study treatment) or if subject is ongoing (not all study treatment discontinuation records completed) or start date is missing. Else assign to 'AFTER' if start date is after the on-therapy period.
- **End relative to treatment:** Assign to 'BEFORE' if end date is prior to study treatment start date or if subject has not taken any study treatment. Else assign to 'DURING' if start date falls into the on-therapy period or if subject is ongoing (not all study treatment discontinuation records completed) or end date is missing and start relative to treatment not 'AFTER'. Else assign to 'AFTER' if start date is after the on-therapy period or end date is missing and start relative to treatment='AFTER'.

Only on-therapy blood and blood supportive care products that start after the start of study treatment are included in the Blood Products and Blood Supportive Care Product summaries. Therefore, for summary tables, include blood and blood supportive care product records where start relative to treatment in ('DURING') and end relative to treatment in ('DURING','AFTER'). All data will be reported in listings.

Concomitant medication start relative to treatment and end relative to treatment flags are used to select data to include in the Concomitant Medication summaries as follows:

- **Summary of Concomitant Medications:** This summary will contain medications including those with start date prior to study treatment start date and which continue (missing end date or end date after study treatment start date) on therapy. Note that any medications with start date and end date prior to study treatment start date will be excluded. In addition, any medication that was started during post-therapy will be excluded. Include concomitant medication records where start relative to treatment in ('BEFORE','DURING') and end relative to treatment in ('DURING','AFTER').

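### SAP 2.1.3.11: the end-of-medication flag tests the start date, so in subjects with completed discontinuation records some medications that ended during or after therapy fall out of the concomitant-medication summary

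*SAP*

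**What the plan says.** SAP 2.1.3.11 derives two flags per record, one placing the start and one placing the end relative to therapy. The on-therapy period is "defined as the time from first dose of study treatment to the last dose date of study treatment".

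The end flag has three branches, taken in order:

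- BEFORE: "Assign to 'BEFORE' if end date is prior to study treatment start date or if subject has not taken any study treatment". This tests the end date.
- DURING: "Else assign to 'DURING' if start date falls into the on-therapy period". Two other routes into DURING follow: the subject is ongoing, meaning that not all study-treatment discontinuation records are complete, or the end date is missing and the start flag is not AFTER.
- AFTER: "Else assign to 'AFTER' if start date is after the on-therapy period or end date is missing and start relative to treatment='AFTER". Apart from the missing-end route, this again tests the start date.

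The concomitant-medication summary keeps records with a start flag of BEFORE or DURING and an end flag of DURING or AFTER. The same paragraph states the intent in prose: "This summary will contain medications including those with start date prior to study treatment start date and which continue". It explains that continuing covers both an absent end date and one later than the start of treatment. The blood-product summary needs a start flag of DURING and an end flag of DURING or AFTER.

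SAP 5.1.2 says the reference variables separate before, during and after for both the start and the end dates. It then adds that the derived variables are not required for reporting these data.

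**The concern.** A flag meant to place the end of a medication should look at its end date. Only the BEFORE branch does. The wording of the other two closely matches the start-flag rule printed directly above, which suggests a copying slip.

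The slip has a consequence because the flag selects records. A record that fits none of the three branches has a blank end flag and fails the filter. The records at risk include a class that the SAP's own prose says must be shown: medication the subject was already taking at first dose and stopped later. Protocol 6.1 requires medications taken in the two weeks before treatment to be recorded, so such records are to be expected. The loss is also selective: a baseline drug with no end date stays in, while one with a documented stop during or after therapy goes out. SAP section 1 gives execution to staff named separately from the author (name redacted), so the literal wording matters.

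**Working it through.** There is no figure in the plan to reproduce; the check applies the written rule to every case.

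**Inputs (SAP 2.1.3.11).** The start-flag rule, the end-flag rule, the on-therapy period and the two summary filters. Under the start-flag rule a missing start date gives DURING, unless the end date precedes treatment, which gives BEFORE. SAP 5.1.2 imputes partial medication dates but not completely missing ones, so "missing" below means wholly missing.

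**One case traced.** Let therapy run from day 0 to day 100. A drug starts on day -10 and ends on day 50, and the subject's discontinuation records are complete.

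1. Start flag: the start precedes first dose, so BEFORE.
2. End flag, BEFORE branch: day 50 is not before day 0, so it fails.
3. End flag, DURING branch: the start, day -10, is not within days 0 to 100; the subject is not ongoing; the end date is present. It fails.
4. End flag, AFTER branch: the start, day -10, is not after day 100; the end date is present. It fails.
5. The end flag is blank, the filter fails, and the record is excluded. The SAP's prose includes it, because it began before treatment and ended after treatment start.

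**All feasible cases, treated subject with discontinuation records complete.** The last two columns test the end date in the DURING and AFTER branches.

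| Start | End | Start flag | End flag as written | In summary as written | End flag, end date tested | In summary, end date tested |
|---|---|---|---|---|---|---|
| before | before | BEFORE | BEFORE | no | BEFORE | no |
| before | during | BEFORE | none | **no** | DURING | yes |
| before | after | BEFORE | none | **no** | AFTER | yes |
| before | missing | BEFORE | DURING | yes | DURING | yes |
| during | during | DURING | DURING | yes | DURING | yes |
| during | after | DURING | DURING | yes | AFTER | yes |
| during | missing | DURING | DURING | yes | DURING | yes |
| after | after | AFTER | AFTER | no | AFTER | no |
| after | missing | AFTER | AFTER | no | AFTER | no |
| missing | before | BEFORE | BEFORE | no | BEFORE | no |
| missing | during | DURING | none | **no** | DURING | yes |
| missing | after | DURING | none | **no** | AFTER | yes |
| missing | missing | DURING | DURING | yes | DURING | yes |

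Of 13 cases, four have no end flag and are dropped. One more (start during, end after) carries the wrong label but is still included. The other eight are unchanged.

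**Blood products.** That filter needs a start flag of DURING, so records begun before therapy are excluded by design. The two cases with a missing start date and an end during or after therapy have a start flag of DURING but no end flag, so they are lost here too. Testing the end date restores them.

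**Ongoing subjects.** The ongoing route gives DURING before any blank can arise. None of the eight feasible cases changes.

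**The case against.** The strongest reply is that the effect is narrow and the intent plain. Much of this stands.

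- **Scope.** Ongoing subjects keep all the relevant records, and a missing end date also leads to inclusion. Under SAP 2.1.1 a medication ending after the cut-off is reported as continuing with no end date imputed, so it appears to follow the missing-end route as well.
- **Counting.** SAP 2.4.2 counts each subject once per ingredient. A dropped record alters the table only if that subject has no other retained record of the same ingredient.
- **Visibility.** Medications are also listed, and SAP 2.1.2 puts all available data in the listings.
- **Intent.** The prose on the summary and SAP 5.1.2 both show what was meant, so a programmer might notice the conflict. That lowers the risk but does not correct the rule, and no other section does.

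A reader might infer that nearly every subject is affected at the final analysis. The documents do not support this. They count neither the subjects with complete discontinuation records nor the pre-existing medications with a recorded later end. SAP 5.1.3.2 expects that some subjects who finish 24 weeks may still be taking lapatinib and capecitabine, so finishing 24 weeks is not the same as having discontinued.

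A reader might also infer that drugs acting on the bowel are lost and the comparison of arms is distorted. Nothing shows that such drugs fall in the affected group, and any medication with a recorded start during therapy, including an anti-diarrhoeal, is retained. The protocol's anti-diarrhoeal-medication endpoint (Table 7) is not in the reduced list in SAP Table 1-3, and the primary endpoint is built from adverse-event records (SAP 2.5.2.1).

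**Conclusion.** The point holds as an internal contradiction in SAP 2.1.3.11. Followed literally, the end-flag rule excludes from the concomitant-medication summary records that the same section says it contains, and it loses some records with missing start dates from both summaries.

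The conclusion applies to treated subjects whose discontinuation records are all complete, and assumes the program follows the text. The number of records cannot be determined. Among pre-existing medications with a recorded end during or after therapy, the share dropped could be anything from none, if all those subjects are ongoing, to all, if all have complete discontinuation records.

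For medications begun before treatment, the rule contradicts the prose directly. For missing start dates the prose is silent; there the fault is that the start flag admits the record and the end flag leaves it unclassified.

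This is a minor drafting error with a real effect on descriptive tables. Listings and efficacy endpoints are not affected.

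**What to change.** In the end flag of SAP 2.1.3.11, change the first condition of both the DURING and the AFTER branch so that it tests the end date, and make the program match. Every combination in the table above then receives a flag. The four dropped cases return, and records wholly before or wholly after therapy stay out, as the SAP intends.

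Also reconcile SAP 5.1.2 with 2.1.3.11: the former says these variables are not needed for reporting, while the latter uses them to choose the records reported.

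The cost is one word in each of two branches, one clarifying sentence, and a check of the derivation code. No new data are needed.

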2.2 Analysis Populations

Intent-to-Treat Population

The Intent-to-Treat (ITT) population will comprise all randomised subjects regardless of whether or not treatment was administered. This population will be based on the treatment to which the subject was randomised. Any subject who receives a treatment randomization number will be considered to have been randomised. The primary analysis of disease efficacy and all diarrhoea-related efficacy endpoints will be analysed using the ITT population.

Modified ITT

The modified ITT (m-ITT) population will comprise all subjects in the ITT population and under Octreotide arm this population will include subjects who do not show intolerance to octreotide in the s.c. formulation and who do not have non treatment related diarrhoea recorded

as an AE after the first dose of octreotide LAR and prior to the start of treatment with lapatinib and capecitabine. A sensitivity analysis of diarrhoea-related primary efficacy endpoint will be conducted using the m-ITT population.

Per Protocol Population

The Per-Protocol (PP) population will comprise all randomised subjects who receive at least one dose of study treatment and who comply closely with the protocol (that is subjects who are not excluded from PP set as per PDMP). The PP population will not be analysed if this population comprises more than 95% or less than 50% of the ITT population. The analysis of primary efficacy endpoint will be repeated using the PP population.

Subjects with potential PDs will be excluded from PP population based on Protocol Deviation Management Plan (PDMP).

Safety Population

The Safety population will comprise all randomised subjects who receive at least one dose of study treatment and will be based on the actual treatment received if this differs from that to which the subject was randomised. This population will be used for the analysis of clinical safety data. Moreover, if a subject who was randomised to Octreotide arm, showed intolerance to octreotide in the s.c. formulation, and took at least one dose of lapatinib or capecitabine, then subject will be included in no Octreotide arm for safety analysis.

